4.2 Device Description

The WaveCrest device is designed to occlude the left atrial appendage (LAA) and consists of the following components: the device, which is pre-loaded on the delivery system, and the Delivery Sheath which is packaged separately. The device, consisting of a separate occluder and anchors, is the implantable component of the system. The device is constructed from a laser-cut nitinol framework. Parts of this framework are constructed with titanium components and also contain tantalum radiopaque markers. The occlusive membrane is composite construction. The surface of the membrane that is exposed to the left atrium is covered with ePTFE and is designed to resist thrombus buildup. The surface of the membrane that is exposed to the LAA consists of polyurethane foam, which is designed to promote rapid tissue growth.

Figure 1: Coherex Left Atrial Appendage Implant

Figure 2: Coherex Left Atrial Appendage Implant and Handle

	Title: WAVECREST Post Market Clinical Follow-Up (PMCF) Study	Doc. #: CHX_IP015	Rev: D
---	---	-----------------------------	------------------

The delivery system for the implant consists of a delivery catheter and a proximal control handle. The delivery catheter is constructed from polyurethane extrusions, stainless steel components, and polyester and PTFE materials that are common to medical catheter construction. The proximal control handle is designed to actuate the anchors through the catheter and to detach the implant from the system. The Coherex WaveCrest® Left Atrial Appendage Occlusion System Delivery Sheath is designed to facilitate the delivery of the implant. The Delivery Sheath includes a dilator used for insertion. The Delivery Sheath is designed to be used exclusively with the Coherex WaveCrest Left Atrial Appendage Occlusion System.

The implant is delivered percutaneously via the femoral vein through a transseptal puncture into the LAA. A separate transseptal puncture system is required. The occluder is designed to be unsheathed inside the ostium of the LAA. When unsheathed, only the occlusive portion of the device is exposed. The structure of this portion is very soft to reduce the risk of perforation or effusion. The occluder may be positioned within the LAA to achieve optimal occlusion. After positioning, the occluder is anchored in place by extending the anchors from the central hub of the device. A distal injection port allows contrast to travel through the delivery system to the distal side of the occluder to allow visualization of the position, stability and effectiveness of occlusion prior to release with fluoroscopy. Anchoring and occlusion can also be assessed by TEE. When anchoring and occlusion are confirmed, the implant is detached and left within the LAA and the Delivery Sheath along with the Delivery Catheter are removed. The WaveCrest device implant is available in diameter sizes of 22, 27 and 32 mm.

More detailed information on the device can be found in the latest version of the approved Instructions for Use and the updated version of the Investigator’s Brochure.

4.3 Intended Indication

The Coherex WaveCrest Left Atrial Appendage Occlusion System is approved for use for the closure of the left atrial appendage (LAA) in patients with non-valvular atrial fibrillation, who are at increased risk for stroke.

4.4 Device Traceability

To ensure traceability of the WaveCrest devices used within the study, the following information will be documented:

- Model and Lot number
- Date of implant

Process for order, receipt and return of the CE-marked devices is in accordance with the commercial process. A Patient Implant Card will be handed to each patient successfully implanted with the device.

	Title: WAVECREST Post Market Clinical Follow-Up (PMCF) Study	Doc. #: CHX_IP015	Rev: D
---	---	-----------------------------	------------------

5.0 Study Design

5.1 Purpose

This study is designed to confirm the safety and performance of the Coherex WaveCrest LAA Occlusion System in current medical practice through 45 day follow-up following minor system enhancements.

5.1.1 Number of subjects

Up to 65 subjects will be enrolled in the study at up to 15 study sites in Europe.

5.1.2 Estimated study duration

Enrollment in the study will be concluded in approximately 18 - 20 months after the first subject is enrolled. Total duration including follow-up visits is expected to be 22 months.

5.2 Endpoints

Safety and performance of the WaveCrest device through 45 days follow-up will include the following endpoints:

- Composite rate of:
 - All-cause mortality
 - Pericardial effusion requiring intervention
 - Device embolization (major)
 - Device thrombus
 - Ischemic stroke
- Device Success - Device deployed and implanted in the correct position
- Technical Success at implant
 - Occlusion of the LAA
 - No device-related complications
 - No leak >5mm on color Doppler TEE
- Procedural Success
 - Technical success
 - No procedure-related complications except uncomplicated (minor) device embolization (resolved by percutaneous retrieval during the procedure without surgical intervention or damage to surrounding cardiovascular structures)

5.3 Inclusion and Exclusion Criteria

The criteria for implant are in conformity with the current version of the Instructions for Use of the CE-marked device:

	Title: WAVECREST Post Market Clinical Follow-Up (PMCF) Study	Doc. #: CHX_IP015	Rev: D
---	---	-----------------------------	------------------

5.3.1 Inclusion Criteria

1. Non-valvular paroxysmal, persistent, or permanent atrial fibrillation
2. 18 years of age or older
3. LAA anatomy amenable to treatment by percutaneous techniques
4. Risk factors for potential thrombus formation in the LAA
5. Willing to participate in the required follow-up visits and tests
6. Subject has been informed of the nature of the study, agrees to its provisions and has provided written informed consent as approved by the EC at the study site.

5.3.2 Exclusion Criteria

1. Known contraindication to percutaneous transseptal intervention
2. Left atrial appendage anatomy or size that will not allow appropriate implantation of the WaveCrest Implant
3. Intracardiac thrombus or other cardiac abnormality visualized prior to implant that would significantly impact procedural safety
4. Mitral valve stenosis $< 1.5 \text{ cm}^2$ or any stenosis consistent with rheumatic valvular disease or history of mitral valve replacement or repair
5. Known contraindication and/or allergy to nickel
6. Known active bacterial infection (i.e., sepsis, endocarditis)
7. Any known medical condition or overall health of the subject that could adversely affect procedural safety or potentially prevent the patient from completing all study required visits and tests.
8. Pregnant or breastfeeding women due to the risk of exposure to x-rays and medications associated with the implant procedure.

5.4 Subject Population

Patients with non-valvular atrial fibrillation who are at increased risk for stroke.

No subjects belonging to a vulnerable population (see definition of vulnerable population in **Appendix I: Acronyms and Definitions**) will participate in the clinical study.

6.0 Study Procedures

The clinical study shall be conducted in accordance with the CIP reflecting current medical practices and approved IFU. All parties participating in the conduct of the clinical study shall be qualified by education, training, or experience to perform their tasks and this shall be documented appropriately.

The clinical study shall not commence until Coherex Medical receives written approval from the relevant EC of each study site as necessary.

6.1 Site and Investigator Selection

Sites will be selected for this study based on the qualification and experience of the implanting investigator. The implanting investigator must have had experience in transseptal puncture

	Title: WAVECREST Post Market Clinical Follow-Up (PMCF) Study	Doc. #: CHX_IP015	Rev: D
---	---	-----------------------------	------------------

procedures and percutaneous LAA closure techniques. Intended users must have completed the WaveCrest Physician Training program. Investigators must provide a financial disclosure statement and sign an Investigator Agreement and/or a site agreement as applicable. Site selection will also depend on the availability of experienced staff to conduct clinical research. Study personnel will be responsible for administering the Questionnaire for Verifying Stroke-Free Status (QVSFS). The study site will have a neurologist or other study personnel who are trained to administer the Modified Rankin Scale.

6.2 Training of Investigators and Study Personnel

Sponsor will provide training on the Clinical Investigational Plan and Case Report Form (CRF) completion.

Additionally, Sponsor will provide training to echocardiographers assigned to the study. Sponsor training on the WaveCrest implant procedure will include:

- an on-line self-study simulation module which will present device and procedure steps,
- training presentation focusing on anatomical considerations, device details and required procedural steps, and
- table-top training with model to simulate implant procedure steps.

A record of training activities and the completed training process will be kept in a training log provided by the Sponsor.

6.3 Informed Consent

All subjects must sign and date the EC approved informed consent prior to undergoing any study-specific tests, assessments or procedures. Investigator or designated study personnel will explain the nature and scope of the study, potential risks and benefits of participation, and answer any questions from the subject. Study personnel must explain that agreeing to participate in the study and signing an informed consent form does not guarantee study participation. The subject must be provided ample time to read and understand the informed consent form and to consider participation in the clinical study. If the subject agrees to participate, the informed consent form must be signed and dated by the subject. The authorized person obtaining informed consent must sign, and date the informed consent prior to conducting any study-specific tests, assessments or procedures. The consent process, provision of a copy to the subject, and date and time of consent must be documented in the subject's medical records. Subject information may be entered in the CRF only after the subject has provided informed consent.

[figure not shown]
Subject confidentiality will be maintained throughout the clinical study in a way that assures that individual subject data can be tracked back to the source data. For this purpose, a unique subject identification code will be used that allows identification of all data reported for each subject. Data relating to the study may be made available to authorized third parties, provided the data are treated as confidential and that the subject's privacy is guaranteed.

A Delegation of Authority Log and a Sponsor-Representative Log will be maintained and updated throughout the study to indicate who the authorized persons are for each task within the study and for whom access to patient confidential data is authorized.

6.4 Subject Selection and Screening

Sites may begin screening subjects for the study upon receiving EC approval. Screening for the study must be performed per Inclusion and Exclusion Criteria based on medical records at the study site (**Figure 3** below).

Figure 3: Patient Screening

6.5 Baseline Procedures

- Document medical history
- Perform physical exam (This is referring to the physical examination or ‘check-up’ of the patient for signs of disease or symptoms)
- Blood work (including INR and serum pregnancy (as necessary))
- CHA₂DS₂-VASc score (see **Appendix II** for calculation of CHA₂DS₂-VASc score)

	Title: WAVECREST Post Market Clinical Follow-Up (PMCF) Study	Doc. #: CHX_IP015	Rev: D
---	---	-----------------------------	------------------

- A study staff member who is trained must administer QVSFS (**Appendix III: Questionnaire for Verifying Stroke-Free Status**)
- In the event of history of stroke or TIA or QVSFS score > 0 a trained study staff member must administer the Modified Rankin Scale. (**Appendix IV: Neurologic Assessments**). A visit to the neurologist or physician qualified to perform neurologic assessment is recommended, per physician’s judgment.
- In the event of history of stroke, brain imaging (CT or MRI) results may be collected if brain imaging is done prior to implant as part of routine practice or if imaging was done at the time of the prior stroke (at any time).
- Perform baseline TEE (may be performed immediately prior to the procedure)

6.6 Point of enrollment

Subjects are considered enrolled in the study when the subject has properly signed the approved Informed Consent. If the patient doesn’t meet all of the inclusion criteria or meets one of the exclusion criteria, the subject is considered a screen failure. The appropriate forms in EDC need to be completed.

Subjects are considered enrolled in the study and Intent-to-Treat is established when the subject has properly signed the approved Informed Consent, has met all of the inclusion criteria and none of the exclusion criteria, and the Coherex Delivery sheath has been inserted into the subject’s femoral vein.

If the device is not implanted for any reason, the patient will be considered a Failure to Implant and discontinued from the study.

All adverse events as of enrollment and prior to patient discontinuation will be collected.

Absence of intracardiac thrombus must be confirmed on the TEE performed during the implant procedure. If thrombus is observed, the implant procedure must be postponed. The subject may be rescreened after the thrombus has resolved.

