6.9 Discharge

Before the subject is discharged from hospital:

- Administer QVSFS questionnaire
 - If there is any concern for stroke, a visit to the neurologist or physician qualified to perform neurologic assessment is recommended
- Record antiplatelet and anticoagulant medications.
- Record adverse events, device malfunctions and protocol deviations as appropriate.
- Discharge subject on 75-325mg aspirin daily and 75mg clopidogrel.

Table 4 summarizes the post-procedure anticoagulation and antiplatelet regimen.

Note: Subjects who are not implanted with a device should be followed through hospital discharge for adverse events and appropriate CRF to be completed.

	Title:	Doc. #:	Rev:
	WAVECREST Post Market Clinical Follow-Up (PMCF) Study	CHX_IP015	D

6.10 45-Day Office Visit (\pm 15 days)

At the 45-day office visit:

- Perform physical exam (This is referring to the physical examination or ‘check-up’ of the patient for signs of disease or symptoms).
- Study personnel must administer the QVSFS;
 - If QVSFS score $>$ 0, a visit to the neurologist or physician qualified to perform neurologic assessment as soon as possible following QVSFS administration is recommended. The modified Rankin stroke scales should be administered by trained study personnel.
- Perform a TEE following the Echocardiography Protocol.
- If patient has been on anticoagulation, cessation of anticoagulation is at physician discretion provided flow around the implant, with correlate 2D residual gap, is demonstrated on TEE to be \leq 5mm. At the time the subject stops anticoagulation clopidogrel 75mg daily should be started and should continue until 90 days post-implant (prasugrel or ticagrelor may be used in place of clopidogrel, but must not be used with anticoagulation).
- Instruct subject to remain on 75 -325 mg aspirin indefinitely. **Table 4** summarizes the post-procedure anticoagulation and antiplatelet regimen.
- Record antiplatelet and anticoagulant medications.
- Record protocol defined adverse events, device malfunctions and protocol deviations as appropriate.

The schedule of assessments is listed below in **Table 3**.

Table 3: Schedule of Assessments

Assessment	Screening/ Baseline	Treatment Visit (Through discharge)	45 Day Visit \pm 15 days
Medical history	X		
Physical exam*	X		X
Pre-Procedure blood work	X		
CHA ₂ DS ₂ -VASc score	X		
TEE	X	X	X
QVSFS	X	X	X
Antiplatelet and Anticoagulant Medication Review	X	X	X
Adverse Event Monitoring ^a	X	X	X

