6.12 Subject Discontinuation

Participation in any clinical study is voluntary and the subject has the right to withdraw at any time without penalty or loss of benefit. Possible reasons for discontinuation may include but may not be limited to the following:

- Voluntary withdrawal
- Participation is terminated by the investigator, although the subject consented, since participation is no longer medically appropriate
- Lost-to follow-up (defined below)

If a patient decides to withdraw from the study, effort must be made to continue monitoring for adverse events even if he/she declines to continue in the study. Discuss with the patient if he/she agrees with phone follow-up only for the purpose of recording adverse events or non-invasive review of records.

Subjects who discontinue participation prematurely will be included in the ITT analysis of results (safety and performance as appropriate) but will not be replaced.

Investigators must report subject withdrawals to their respective EC as defined by their institution's procedure.

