8.0 Adverse Event, Adverse Device Effect, Device Deficiency

8.1 Adverse Event (AE)

An adverse event is any untoward medical occurrence, unintended disease or injury, or untoward clinical signs (including abnormal laboratory findings) in subjects, users or other persons, whether or not related to the device. This definition includes events related to the procedures involved.

Note: Unchanged, chronic, non-worsening or pre-existing conditions are not adverse events.

The investigator must monitor and report the occurrence of adverse events for each subject. Adverse events, including the event description, date of onset, outcome, whether or not any medication changed or a hospitalization or intervention occurred, and whether the adverse event was resolved (if so, how, and date of resolution), must be reported on the appropriate CRF within 2 weeks. Every effort must be made to report the underlying condition or unifying diagnosis for the event. To avoid vague, ambiguous, or colloquial expressions, adverse events should be recorded in standard medical terminology rather than the subject's words. The appropriate CRF must be updated as additional information on the event is received.

	Title: WAVECREST Post Market Clinical Follow-Up (PMCF) Study	Doc. #: CHX_IP015	Rev: D
---	---	-----------------------------	------------------

All events must be followed until resolution or until a stable clinical endpoint is reached. The medical safety officer may decide if more follow up information is needed in case the event is not resolved at study completion.

Relatedness

For each event, the investigator will assess relationship to the device and the implant procedure. Relationship of an adverse event to the device and/or implant procedure will be based on assessment of temporal relationships, biologic plausibility, association (or lack of association) with underlying disease and presence (or absence) of a more-likely cause. Device and procedure relationship of each adverse event will be categorized according to five different levels of causality, adapted from MEDDEV guideline 2.7/3 rev 3 and as defined below:

- **Not related:** relationship to the device or procedure can be excluded when:
 - the event is not a known side effect of the product category the device belongs to or of similar devices and procedures;
 - the event has no temporal relationship with the use of the device or the procedures;

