8.8 Reporting requirements

Adverse events are reported beginning from the time the patient is enrolled until patient participation has ended.

The investigator shall inform the Sponsor of all adverse events and device deficiencies as described in table below:

Event Classification	Recording Method	Timeline
Adverse Events, including ADE	Complete appropriate CRF form	As soon as possible or as per local regulations, but no later than 2 weeks of site awareness
Serious Adverse Events, including SADE	Complete appropriate CRF form Provide all necessary documentation needed	Immediately upon awareness of the event or became aware that the event met the definition of a SAE, but no later than 72 hours
Death	Complete appropriate CRF form	Within 24 hours
UADE	Complete appropriate CRF form	Immediately upon awareness of the event, but no later than 24 hours
Device deficiencies	Complete appropriate CRF form	Within 24 hours

The investigator is responsible for informing the EC of adverse events as required by local reporting requirements.

The Sponsor will submit on regular basis (unless otherwise indicated by the EC or recommended by the Sponsor's medical safety officer) to all participating investigators an update of reported events and device deficiencies occurred at the participating study site.

The Sponsor will ensure that all events and device deficiencies are reported to the relevant authorities per country specific regulations.

The Sponsor will continue safety surveillance and safety reporting until the last follow-up visit has been performed, the subject is deceased, the subject/investigator concludes his participation in the study or the subject/investigator withdraws the subject from the study.

The Sponsor is responsible for the classification of adverse events and shall review the investigator's assessment of all adverse events.

The Sponsor will determine and document in writing their seriousness and relationship to device.

	Title: WAVECREST Post Market Clinical Follow-Up (PMCF) Study	Doc. #: CHX_IP015	Rev: D
---	---	-----------------------------	------------------

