### 7.3 Safety Endpoint

The safety endpoint for the investigation is a composite of the following through 45 days follow-up post implant:

- All-cause mortality
- Pericardial effusion requiring intervention
- Device embolization (major)
- Device thrombus
- Ischemic stroke

All safety events occur within the 45 days follow up visit window (up to Day 60) will be adjudicated by the Sponsor. The safety endpoints analysis will be based on Sponsor Assessment of Adverse Events data. No formal statistical inference will be made. The analysis will be descriptive for the ITT analysis set. The number and percentage of subjects experiencing any occurrence of the composite safety endpoint will be summarized assuming binomial distribution. The exact two-sided 95% confidence intervals will be constructed for the composite endpoint. A similar analytical approach will be performed for each component as well.

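### Failed implants stay in the 45-day ITT safety composite but are followed only to hospital discharge, with no denominator rule; treated subjects later found ineligible fall outside both analysis sets

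*Protocol*

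**What the plan says.** **Who is analysed.** Protocol 6.6 and SAP 5.1 place a subject in ITT on three conditions: consent, all eligibility criteria satisfied, and the Delivery Sheath in the femoral vein. An implant is not required. SAP 5.2 takes As-Treated from within ITT. SAP 7.3 analyses the composite in ITT only; SAP 7.4 and 7.5 use both sets. Protocol 6.12 adds: "Subjects who discontinue participation prematurely will be included in the ITT analysis of results".

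**How long failed implants are observed.** Protocol 6.6: "If the device is not implanted for any reason, the patient will be considered a Failure to Implant and discontinued from the study". The same section limits adverse event collection to the time before discontinuation. The note in Protocol 6.9 reads: "Subjects who are not implanted with a device should be followed through hospital discharge for adverse events". Protocol 8.8: "Adverse events are reported beginning from the time the patient is enrolled until patient participation has ended". Continued contact is foreseen in Protocol 6.12 for one group: "If a patient decides to withdraw from the study, effort must be made to continue monitoring for adverse events". Protocol 8.1 covers events already under way: "All events must be followed until resolution or until a stable clinical endpoint is reached".

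**Time frame.** SAP 7.3 opens with "The safety endpoint for the investigation is a composite of the following through 45 days follow-up post implant" and then says "All safety events occur within the 45 days follow up visit window (up to Day 60) will be adjudicated by the Sponsor". SAP 2.1 and 3.0 give 45 days plus or minus 15. SAP 7.4 and 7.5 give plus 15. Protocol 5.2 says through 45 days, and Protocol 13.2 summarises at the 45-day time point.

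**Missing data.** SAP 6.3 imputes nothing and works with the data observed.

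**The concern.** A subject with a failed implant has had the venous access and the procedure, and is counted in a 45-day proportion, but is watched only until discharge. Death, stroke and late effusion do not need an implant to occur. The protocol itself treats the period after discharge as relevant: section 3.5 justifies 45 days as long enough to capture procedural safety events, and section 8.1 generally presumes that an event within 30 days is procedure-related unless there are clear signs otherwise.

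The eligibility condition raises a second problem. If a subject is treated and later found not to have met a criterion, SAP 5.1 read literally removes that subject from ITT, and SAP 5.2 then removes the subject from As-Treated. No other set exists, so an event there would be listed (SAP 6.1 lists data for all enrolled subjects) but would enter no rate or table.

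Both rules can only reduce the number of events counted, in a study where very few are expected. The unclear status of Day 46-60 events is a lesser matter of wording. It bears mainly on device thrombus, which is looked for on a TEE that may be done as late as Day 60.

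**Working it through.** **1. The plan's own figure.** Protocol 13.1 and SAP 7.1 assume a 5% composite rate, a two-sided exact 95% interval with upper limit below 15%, and 10% drop-out.
- 0.05 × 56 = 2.8, rounded to 3 events. Clopper-Pearson for 3/56 = 5.4%: 1.1% to 14.9%. With 3/55 the upper limit is 15.1%, so 56 is the smallest size that meets the target with 3 events.
- 56/0.9 = 62.2, rounded up to 63. Both stated figures reproduce.
- Expected events among 63: 63 × 0.05 = 3.15.

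**2. What one event does** (exact 95% limits).

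| Events/N | Rate | Upper limit |
|---|---|---|
| 2/63 | 3.2% | 11.0% |
| 3/63 | 4.8% | 13.3% |
| 4/63 | 6.3% | 15.5% |
| 3/62 | 4.8% | 13.5% |
| 3/60 | 5.0% | 13.9% |

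One uncollected event turns 4/63 into 3/63. One event in a subject dropped as ineligible turns 4/63 into 3/62. Removing three event-free failed implants turns 3/63 into 3/60, a much smaller shift.

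**3. How likely a missed event is.** The documents give no failed-implant count. The nearest figure is the limited market release (Protocol 3.4): 88/92 procedural successes, so 4 failures. Then 63 × 4/92 = 2.7, about 3. This is only a proxy, since a procedural failure may be an implanted subject with a complication. Let k be the number of failed implants and p the risk of a component event beginning after discharge; both are assumptions.
- Expected missed events = k × p: 3 × 0.02 = 0.06.
- Chance of at least one = 1 − (1 − p)^k: 1 − 0.98³ = 5.9%.
- Low end, k = 1 and p = 0.01: 1.0%. High end, k = 5 and p = 0.05: 1 − 0.95⁵ = 22.6%.

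**4. Denominator.** Protocol 6.12 keeps discontinued subjects in ITT, which implies that a failed implant with no recorded event counts in effect as event-free. SAP 6.3 could instead be read as removing that subject. The drop-out allowance from 56 to 63 also suggests an evaluable number below enrolment. No sentence chooses between the two.

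**5. Day 46-60.** The limited release found device thrombus in 2/92 on a follow-up TEE, day not given. At that rate, 63 × 2/92 = 1.37 are expected. If 25% to 50% of TEEs fall after Day 45 (assumption), 1.37 × 0.25 = 0.34 to 1.37 × 0.50 = 0.68 events depend on the cut-off. Leaving one out turns 3/63 into 2/63.

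**The case against.** The case against is substantial in parts.

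- *Failed implants are not simply scored as event-free.* A reader might infer that they are. The documents do not support that as a stated rule, because SAP 6.3 leaves room for removing them. What stands is that post-discharge events are not collected under either reading and that the denominator is unstated.
- *The loss is small.* This is right: about 0.06 expected events on the central assumption. In-hospital events are collected, events already begun are followed under Protocol 8.1, and a subject without an implant cannot have thrombus on a released device.
- *The ineligible-subject problem is hypothetical.* No passage describes reclassifying a treated subject, and the criteria can be read as judged when the sheath goes in. A reader might go further and suppose that anatomical implant failures would be relabelled ineligible and removed; nothing in the documents says so. The gap follows from the literal wording only, its frequency is unknown, and the events would remain in listings.
- *The SAP mostly points to Day 60.* SAP 3.0, the adjudication sentence in 7.3, and 7.4 and 7.5 favour counting to the end of the window. This is therefore loose wording, at odds with the opening of SAP 7.3 and with Protocol 5.2 and 13.2, rather than a rule that loses events. Protocol 3.4 also reports no safety-related events after 45 days for Version 1.3.

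**Conclusion.** The concern holds in limited form. By explicit rule, failed implants belong to the 45-day ITT composite but are observed only to discharge, and the denominator rule is missing. By literal wording, a treated subject later found ineligible is in neither analysis set. The Day 46-60 question needs only consistent wording.

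The chance that failed implants hide at least one event is about 6%, with a range of 1% to 23%. This rests on assumed numbers of failed implants (1 to 5) and post-discharge risks (1% to 5%), none of which the documents give. No probability can be put on the ineligible-subject case. If one event were missed, the reported result would read 4.8% (upper limit 13.3%) instead of 6.3% (15.5%).

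A reader might infer that crossing 15% would change the study's conclusion. It would not: SAP 7.3 makes no formal inference, and 15% is a planning target, not a decision rule. What is at stake is the accuracy of the main safety rate. The matter should be fixed because the remedy is cheap and both collection gaps act in the same direction, towards fewer counted events.

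**What to change.** - **Analysis set (SAP 5.1, Protocol 6.6).** Analyse the composite, the success endpoints and adverse events in all consented subjects with the Delivery Sheath inserted, whatever is later found about eligibility. At minimum, add this as an all-treated set. List eligibility violations as deviations.
- **Status check (Protocol 6.6, 6.9).** For failed implants, and for subjects whose visit precedes the cut-off (participation ends with the completed visit under Protocol 6.14), collect vital status and adverse events at the cut-off by phone or record review. Protocol 6.12 already uses that route for withdrawals. If follow-up is closed, report how many subjects were incompletely observed and their last day observed.
- **Time frame and denominator.** Count from the procedure date, since a post-implant origin gives failed implants no start. State one cut-off, Day 60, the upper end of the visit window, and use the same wording in Protocol 5.2 and 13.2 and SAP 2.1, 3.0, 7.3, 7.4 and 7.5. State that every subject in the set stays in the denominator and that SAP 6.3 does not remove anyone from the composite.
- **Sensitivity analysis.** Restrict to subjects observed to the cut-off or with an event. If no Day 60 check is made, require observation to at least Day 30, the start of the window. A Day 45 requirement would mislead: if 25% to 50% of visits fall after Day 45, it keeps all the events but only about 16 to 32 of 63 subjects, so 3 events would read as roughly 3/16 = 18.8% or 3/32 = 9.4%.

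A separate inconsistency: Appendix II sets a minimum CHA₂DS₂-VASc score that does not appear in Protocol 5.3.1. The passages must be reconciled.

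**Cost:** at most one short call or record check per subject (65 at most), wording changes and one sensitivity analysis. The reported rate may be slightly less favourable. If follow-up is closed, only the set definition, wording and reporting change.
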